799 are assessed every 6 months from baseline to 5 years of therapy. Thus, analyses of bone biopsy endpoints
800 involve both within-arm and between-arm comparisons at the 3 times, while all other analyses will utilize
801 standard repeated measures methods for longitudinal data.

802 These analyses will initially include all randomized subjects who remain evaluable for the endpoints,
803 including those eligible out of the subjects currently on conventional therapy plus the 36 newly enrolled
804 subjects. However, if covariate adjustment in analyses described below indicates that there are differences
805 between these strata, then the 3 strata will be analyzed separately. The subjects who were on HPTH under
806 the previous version of the protocol will be analyzed separately using similar analysis methods,
807 recognizing the limitations of the small sample size (≤ 8). Any subject who enters menopause prior to the
808 second bone biopsy will remain in the study and will undergo the second biopsy; however, the results will
809 be reported separately and not included in the data analyses of the randomized groups. It is felt that
810 reviewing the results from a menopausal woman anecdotally may give insight into possible treatment
811 effects in a menopausal sub-population. Data will be summarized graphically and in tabular form using
812 standard descriptive statistics for categorical and continuous measures, with appropriate consideration of
813 underlying distributional assumptions. All tests of significance will be two-tailed at the 0.05 level.

814 For the bone biopsy endpoints, paired t-tests will be used to test the hypotheses that the 1, 2, and 4-year
815 changes from baseline are significantly different from zero. One-way analysis of variance (ANOVA) will
816 be used to compare these differences to each other, with protected individual linear contrasts performed if

817 the overall F-test is significant. The effects of selected baseline covariates, including gender and
818 menopausal status, will be assessed using analysis of covariance (ANCOVA) in a sensitivity analysis.
819 Exploratory graphical methods will also be used to assess distributional assumptions and potential
820 differences in responses between the strata. Log-transformation of raw data or non-parametric test
821 alternatives may be considered if indicated by these exploratory analyses.

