871 between-biopsy-arm comparisons. With 8 new subjects per arm, there is 75% power to detect a
872 significant difference in mineralizing perimeter with a two-tailed 0.05 level overall F-test if the 3
873 differences from baseline are, for example, 10%, 15% and 21%, assuming a within-group standard
874 deviation of 7%. Similar results were obtained for bone formation rate.

875 Finally, based on current experience, the dropout rate of subjects on HPTH therapy for 5 years could be as
876 high as 1 in 3 (33%). To account for that, 36 new eligible subjects will be randomized to the 3 biopsy
877 follow-up time arms, which should result in at least 24 new subjects being evaluable for the primary
878 analyses of the bone biopsy endpoints at years 1, 2 and 4. Up to 10 additional subjects may be screened
879 but not enter the treatment or randomization phase.

880 **10.3 Randomization and Stratification**

881 While there is only one treatment group, subjects will be randomized 1:1.2:1.4 at baseline to the 3 bone
882 biopsy follow-up times of 1, 2, or 4 years, respectively. Heavier weighting is given to the arms with
883 longer follow-up times as these arms are anticipated to have more dropouts. In addition, the
884 randomization will be stratified on 3 factors, gender (Male/Female), menopausal status (pre / post
885 menopausal), and prior participation in this trial (Yes/No). Stratification on gender is indicated because of
886 known gender-based differences in bone formation. Stratification on menopausal status is indicated
887 because of known hormonal changes that may influence bone mineralization. Stratification on prior
888 participation is indicated because the subjects enrolled under the previous version of the protocol will
889 have their pre-conventional therapy biopsy used as their baseline biopsy (new subjects will have their
890 baseline biopsy at the end of conventional therapy) and the effects of conventional therapy on the biopsies
891 is not known with certainty. In order to avoid potential loss of power in the primary analyses if these 3
892 strata are found to be different, 36 new subjects will be enrolled in one stratum and those eligible to
893 continue from among the 10 currently enrolled subjects will be enrolled in the other stratum.

894 Since the target subject sample size is relatively small and there are 3 binary stratification variables, a

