7.4 Analysis Methods

All study endpoints used in analyses will be summarized in tables. Continuous endpoints will be summarized over time using n, mean \pm se, median, min, max. Endpoints requiring log-transformation will also be summarized over time using geometric means with their 95% confidence limits. Ordinal endpoints will be summarized using medians, min, max, and their 10th and 90th percentiles. Categorical endpoints will be summarized using number and percent in each category.

All efficacy analyses related to the bone biopsies will be performed on the Bone Biopsy Population. All efficacy analyses other than the bone biopsy related endpoints will be performed on the Secondary Efficacy Population.

For subjects who enter menopause during the study, any of their efficacy endpoints collected during or post-menopause will be excluded from the efficacy analyses, and will have such endpoints reported separately in the subject listings.

Unless otherwise stated, all statistical inference will be based on an alpha level of 0.05 with adjustments for multiple comparisons when needed as described below. Analyses will be made using SAS (SAS Institute, Cary, North Carolina), version 9.4 or later.

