7.4.1 Primary Efficacy Analyses

Separate primary analyses will be performed for each of the eight primary bone structure and bone remodeling biopsy endpoints listed in section 7.2.1. Since the study was terminated early and is thus under-powered, no corrections for multiplicity will be made in the analyses of the 8 primary efficacy endpoints. For each of these primary bone biopsy endpoints, the primary analysis will test for differences with respect to the time of the biopsy (baseline, 1, 2, and 4 year). These endpoints will be analyzed using repeated measures mixed models with the bone biopsy endpoint as the dependent variable, the baseline value of the bone biopsy endpoint and study cohort as covariates, biopsy time (baseline, 1 year, 2 year, and 4 year) as the repeated measure, and subject as the random variable. The repeated measures will include a time-dependent covariate to adjust the baseline biopsy of Cohort 2 for the time delay between the baseline biopsy and the start of hPTH treatment. This covariate will adjust Cohort 2 for any possible further progression of disease occurring between the baseline biopsy measures and the start of hPTH therapy. An indicator variable in the statistical model will set the effects of this time-dependent covariate to zero for Cohort 3 and for the post-baseline biopsies of Cohort 2.

Pairwise contrasts between the bone biopsy times will be performed within the repeated measures analyses to compare the effects of the biopsy times on the bone biopsy endpoints. Because the sample size for 2-year and 4-year biopsies are reduced in size due to withdrawal and the early termination of the study, the 2-, and 4-year biopsies may be combined into one group provided their effects are qualitatively similar (i.e. the estimates of their effects are in the same direction). If the 2- and 4-year biopsies are qualitatively different then the 4-year biopsies may be dropped from the analysis due to its small sample size. The post hoc pairwise comparisons among the

biopsy time-points will be corrected for multiple comparisons using Fisher's protected LSD with Bonferroni corrections when the overall effect of biopsy year is not statistically significant.

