7.4.2 Secondary Efficacy Analyses

7.4.2.1 Covariate adjustments for dose on the primary efficacy analysis models of the bone biopsy endpoints

The bone biopsy repeated measures analyses described in the primary analyses will be explored further by repeating the same analysis but with hPTH dose as an additional covariate. Four measures of dose will be tested as covariates: 1) average dose over the last 6 months prior to the bone biopsy or weaning whichever comes earlier; 2) average dose per kg body weight over the last 6 months prior to the bone biopsy or weaning whichever comes earlier; 3) total daily dose across the whole study up to the time of the bone biopsy or weaning whichever comes earlier; and, 4) total dose per kg of body weight across the whole study up to the time of the bone biopsy or weaning whichever comes earlier. The effects of these dose measures on the bone biopsy results will be modeled separately fitting both linear and quadratic (curvilinear) effects for the dose variable. The best covariate models will be selected based upon examination of the residuals and comparison of the Schwarz-Bayesian criterion.

The relationships between dose and bone biopsy endpoint will be graphically illustrated using scatterplots of the bone biopsy endpoint over dose with appropriate regression lines.

7.4.2.2 Sensitivity analyses of female menopause status in the primary bone biopsy efficacy models

Sensitivity analyses will be performed to test the effects menopause status in females on our best primary efficacy bone biopsy repeated measures models (with or without dose covariates, sections 7.4.1 and 7.4.2.1). Menopause status will be tested as a covariate in the statistical models (excluding males). The covariate for menopausal status will be parameterized into a categorical variable with 2 levels: 1) pre-menopausal female; and 2) menopausal or post-

menopausal female. If the data is rich enough, further exploratory analyses may test for interactions between dose, and menopausal status. Best models will be selected based upon residual analysis and the Schwarz-Bayesian criterion. Results will be summarized in tables.

7.4.2.3 Changes in bone mineralization density based on back-scattered electron imaging of bone-biopsies

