7.4.2.4 Repeated measures analyses of the non-biopsy secondary endpoints

The secondary non-biopsy secondary endpoints are listed in section 7.2.2.

Unlike the biopsy endpoints, the secondary non-biopsy secondary endpoints had measurements at baseline and then every 6 months over the 5 years of the study as compared to biopsies at baseline, 1, 2, and 4 years of hPTH treatment. As a complication, subjects were on hPTH therapy for various lengths of time due to study withdrawal and early study termination. Thus, the effects of study month are not the same for each subject with some subjects on hPTH therapy and some

subjects off hPTH therapy for the later study months. Thus, the 6-month time-points will be reduced to the following experimental time-points: baseline visit, 6-month study visit, end of hPTH therapy, and post-hPTH follow-up visit.

The effect of hPTH therapy over the experimental time-points (baseline, 6-month study visit, last hPTH treatment, and post-hPTH follow-up) on each of the non-biopsy endpoint parameters will be analyzed using repeated measures mixed models with the non-biopsy endpoint as the dependent variable, the baseline value of the non-biopsy endpoint, and study cohort as covariates, the experimental time-point as the repeated measure, and subject as the random factor. If dose is found to improve model fits in the bone-biopsy repeated measures analyses (section 7.4.2.1) then the effect of dose will be added as a covariate to these secondary repeated measures. Pairwise post hoc comparisons will be made to test for endpoints differences among the experimental time-points (baseline, 6-month study visit, last hPTH treatment, and post-hPTH follow-up). The significance of these post hoc pairwise comparisons will be corrected for multiple comparisons using Fisher's protected LSD. When the repeated measures overall effects of study time-point are not significant, Bonferroni corrections will be used to adjust the pairwise contrasts for multiplicity.

Residual analysis will be used to confirm that repeated measures model assumptions are reasonable. Log-transformations of the bone biopsy endpoints will be made if indicated by the residual analysis. The repeated measures will be fit using both a compound symmetry and an unstructured covariance structure. The better covariance structure will be selected as the model with the better Schwarz- Bayesian criterion.

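### If the 2- and 4-year biopsies are pooled, a cumulative-dose covariate is the only term left that separates them, so much of any shared year-2 to year-4 change would be credited to dose

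*SAP*

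**What the plan says.** SAP 7.4.1 models each primary biopsy endpoint with baseline value, cohort and biopsy time (baseline, 1, 2 and 4 years). The later groups are small, so for years 2 and 4 the section adds that they "may be combined into one group provided their effects are qualitatively similar (i.e. the estimates of their effects are in the same direction". Equal size is not required. SAP section 9 repeats that this merging will be evaluated because of early termination.

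SAP 7.4.2.1 then fits the same model with a dose covariate, linear and quadratic. Measures 1 and 2 are averages over the last six months. Measure 4 is "total dose per kg of body weight across the whole study up to the time of the bone biopsy or weaning whichever comes earlier". Measure 3 is "total daily dose across the whole study up to the time of the bone biopsy or weaning whichever comes earlier", which can be read as a running total or as a daily mean. Models are chosen by residuals and the Schwarz-Bayesian criterion.

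The result is used again. SAP 7.4.2.4 begins a rule with "If dose is found to improve model fits in the bone-biopsy repeated measures analyses" and then adds dose to the non-biopsy models, without saying which measure. SAP 7.4.2.2 builds on the best biopsy model, with or without dose.

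On test level, SAP 7.4 says "all statistical inference will be based on an alpha level of 0.05", and Protocol 10.1 says "All tests of significance will be two-tailed at the 0.05 level".

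**The concern.** Cumulative dose is daily dose multiplied by time on drug. With years 2 and 4 merged, the time factor no longer separates them, but cumulative dose still does. If all subjects drift up or down between year 2 and year 4, the dose coefficient absorbs part of that drift even when daily dose has no effect at all.

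The same-direction rule is a weak guard. A 15% change and a 21% change pass it, and so does a decline from 15% to 9%. The documents use stricter conditions elsewhere. Protocol 10.1 considers pooling follow-up times only when ANOVA shows no significant difference, and SAP 7.4.2.3 asks for similar effect sizes and variances.

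The Protocol Introduction names as unknown whether the skeletal changes persist or return to baseline over time. Reporting a time course as a dose-response would misstate the answer to that question, and the dose term could then pass into the menopause and non-biopsy models.

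**Working it through.** **Inputs from the documents.**
- SD of change in mineralizing perimeter: 7% (Protocol 10.2).
- Year-1, -2 and -4 profile, given only as a power example: "differences from baseline are, for example, 10%, 15% and 21" (per cent). The year-2 to year-4 shift is 21 − 15 = 6 points, or 6/7 = 0.86 SD.
- Planned evaluable subjects: 8 per arm, 24 in all (Protocol 10.2).
- Biopsies obtained: 8 in newly enrolled subjects (SAP section 9), plus at most 10 from the prior conventional-care group (Protocol 10.3). The total is therefore 8 to about 18. The split by year is not given.

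**Assumptions.** Between-subject CV of daily dose is 20–50%. Daily dose is constant within subject and unrelated to response. Splits over years 1/2/4 are 3/3/2 (n=8) and 6/6/6 (n=18), with the planned 8/8/8 for reference.

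**Reproducing the plan's figures.** The mean of 10, 15 and 21 is 15.33, and the squared deviations sum to 60.67. The noncentrality is 8 × 60.67/49 = 9.90 on 2 and 21 df, giving power 74.8% (stated 75%). The paired t-test with n=8 and effect 10/7 gives 93.1% (stated 93%).

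**How much of the shift goes to dose.** Let D = r·t, where r is the dose rate (mean 1, CV c) and t is years on drug. The pooled model is

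change = a + g·[year 2 or 4] + b·D.

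Take equal arms and large samples. In the merged group, D has mean 2 or 4, so its variance between years is 1 and its variance within years averages c²(4+16)/2 = 10c². The year-1 arm adds c². With two merged arms to one year-1 arm, the slope produced by a shift δ is b = (δ/2)·2/(2 + 20c² + c²). The share credited to the two extra years is

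2b/δ = 2/(2 + 21c²), which is 70%, 51% and 28% at c = 0.2, 0.3 and 0.5.

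Small samples give somewhat larger shares, as the simulation shows.

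**Simulation.** No true dose effect, changes 10/15/21, SD 7, and a two-sided 5% test of linear cumulative dose in a change-score regression with years 2 and 4 merged. The first rate in each cell adjusts for baseline (and for cohort where n>8). The second has no such covariates.

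| Split | CV 20% | CV 30% | CV 50% | Share credited (CV 20/30/50%) |
|---|---|---|---|---|
| 3/3/2 | 7.9 / 10% | 8.3 / 9% | 6.3 / 8% | 91 / 75 / 45% |
| 6/6/6 | 19.3 / 21% | 14.6 / 16% | 9.7 / 12% | 77 / 57 / 33% |
| 8/8/8 (not reached) | 24.6 / 28% | 19.3 / 21% | 12.2 / 14% | 74 / 58 / 34% |

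Allowing for variation between runs, the ranges are about 6–11%, 10–22% and 12–29%. A quadratic dose term (2 df) gives 5–15% for n=8–18.

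**Controls.**
- Equal year-2 and year-4 means, pooled: 4–6%.
- Six-point shift, years kept separate: 4–6%, share credited about 0.
- Six-point shift, pooled, last-6-month average dose: 4–6%.
- Six-point shift, pooled, cumulative dose divided by years: about 5%.
- The same-direction rule was met in essentially every simulated trial with the shift.

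**Schwarz-Bayesian criterion.** For n=8–18 it adds dose in 25–44% of pooled runs with the shift, against 15–34% with no shift. At n=18 and CV 20%, the figures are 39% against 16%. Keeping years separate brings that 39% back to 18%.

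**The case against.** The strongest reply is that this is narrow. Pooling is optional. The dose analysis is secondary and described as exploration. Measures 1 and 2 are unaffected, and measure 3 is ambiguous. The primary time analysis contains no dose term, and summary tables by biopsy year are planned, so a year-2 to year-4 difference should stay visible. Carry-over to 7.4.2.2 and 7.4.2.4 is itself conditional. All of this stands and limits the point to a conditional risk.

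The size also rests on inputs the documents do not supply. The dose CV is assumed, the 10/15/21 profile is an illustration, and dose is titrated to serum calcium, so a constant daily rate is a simplification.

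A reader might infer that the plan carries a fixed error rate as high as 37%, or that the whole shared change goes to dose. The documents support neither. A rate of 37% comes from a stacked random-intercept model at 8 subjects per arm, a number not reached. In a check of that type of model at n=8–18, the rate was already about 8–11% without the baseline covariate (14–19% with it) when there was no shift or years were separate. Only the excess can be charged to pooling. The share credited to dose is partial and falls as dose varies more between subjects.

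A 5% test is also not the selection rule in 7.4.2.1. That is fair, but the Schwarz-Bayesian criterion gives no protection. With 8 biopsies it adds dose in about a third of runs even when nothing is there.

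**Conclusion.** The point holds as a conditional confounding risk and is worth correcting. The stated rules permit a model in which cumulative dose alone distinguishes year 2 from year 4. Under the protocol's illustrative shift and SD, with an assumed dose CV of 20–50%, roughly one third to 90% of the shift is then reported as a dose effect. The linear term is falsely significant in about 6–11% of analyses at n=8 and 10–22% at n=18. With equal year-2 and year-4 means there is no inflation. The bias in the coefficient matters more than the error rate, because it does not shrink away at small n, where the test merely has less power to flag it.

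**What to change.** Add to SAP 7.4.2.1: *Any model containing a cumulative dose measure (measure 4, and measure 3 if defined as a total) keeps separate 1-, 2- and 4-year levels of biopsy time, even if years 2 and 4 are combined under 7.4.1. If the combined level must be used, the cumulative measure is replaced by cumulative dose divided by years on hPTH.* State whether measure 3 is a total or a daily mean. Draw the dose scatterplots and regression lines within biopsy year, using on-treatment biopsies only, so that neither zero-dose baselines nor the biopsy year sets the slope.

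The cost is wording and one model degree of freedom, with no new data. That degree of freedom is noticeable in cohort 3 alone: with 8 biopsies, a change-score model with time and linear dose drops from 8 − 3 = 5 to 8 − 4 = 4 residual df. The dose-per-year option avoids this loss.

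The change removes the confounding. It does not make criterion-based selection reliable at very small n: with 8 biopsies and years kept separate, the criterion still adds dose in about 40% of runs.

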7.4.2.4 Repeated measures analyses of the non-biopsy secondary endpoints

The secondary non-biopsy secondary endpoints are listed in section 7.2.2.

Unlike the biopsy endpoints, the secondary non-biopsy secondary endpoints had measurements at baseline and then every 6 months over the 5 years of the study as compared to biopsies at baseline, 1, 2, and 4 years of hPTH treatment. As a complication, subjects were on hPTH therapy for various lengths of time due to study withdrawal and early study termination. Thus, the effects of study month are not the same for each subject with some subjects on hPTH therapy and some

subjects off hPTH therapy for the later study months. Thus, the 6-month time-points will be reduced to the following experimental time-points: baseline visit, 6-month study visit, end of hPTH therapy, and post-hPTH follow-up visit.

The effect of hPTH therapy over the experimental time-points (baseline, 6-month study visit, last hPTH treatment, and post-hPTH follow-up) on each of the non-biopsy endpoint parameters will be analyzed using repeated measures mixed models with the non-biopsy endpoint as the dependent variable, the baseline value of the non-biopsy endpoint, and study cohort as covariates, the experimental time-point as the repeated measure, and subject as the random factor. If dose is found to improve model fits in the bone-biopsy repeated measures analyses (section 7.4.2.1) then the effect of dose will be added as a covariate to these secondary repeated measures. Pairwise post hoc comparisons will be made to test for endpoints differences among the experimental time-points (baseline, 6-month study visit, last hPTH treatment, and post-hPTH follow-up). The significance of these post hoc pairwise comparisons will be corrected for multiple comparisons using Fisher's protected LSD. When the repeated measures overall effects of study time-point are not significant, Bonferroni corrections will be used to adjust the pairwise contrasts for multiplicity.

Residual analysis will be used to confirm that repeated measures model assumptions are reasonable. Log-transformations of the bone biopsy endpoints will be made if indicated by the residual analysis. The repeated measures will be fit using both a compound symmetry and an unstructured covariance structure. The better covariance structure will be selected as the model with the better Schwarz- Bayesian criterion.

7.4.2.5 Summary of the effects of hPTH weaning on serum calcium, phosphorus, calcitriol, and biomarkers of bone turnover.

The effects of weaning subjects off hPTH will be summarized descriptively by the study PI.

Mixed models repeated measures analysis will test treatment effects on 10 outcome measures: serum calcium, serum phosphorus, 3 bone turnover markers (Osteocalcin, n-Telopeptide, and Alkaline Phosphatase), and 5 DEXA Bone Mass Density (BMD) parameters. The DEXA bone mass density measures included: AP spine BMD, femoral neck BMD, total hip BMD, Forearm BMD, and whole body BMD. Treatment effects will be summarized at three study time-points: Baseline (immediately at start of hPTH treatment), Treatment (immediately prior to Weaning, i.e. end of hPTH treatment), and Follow-up. The repeated measures analyses will be performed using each of these 10 outcome measures as the dependent variables, with random effects for subject,

and repeated fixed effects for 3 study time-points within a subject. These outcome measures will be log-transformed if necessary to normalize the data. Two covariance structures will be tested (compound symmetry and unstructured) and the covariance structure with the smallest Bayesian Information Criterion (BIC) and the best residual distributional properties will be used. Pairwise post hoc contrasts will be made to compare the effects of treatment at the study time-points. These post hoc pairwise contrasts will be corrected for multiple comparisons using Fisher's protected LSD with Bonferroni corrections when the overall effect of time is not significant.

Rho will provide figures with panel columns for the subject and the panel rows for the time course (baseline, during hPTH, through the start of weaning to the post-hPTH follow-up) of oral elemental calcium and calcitriol dosing, plasma calcium, and PTH dose.

7.4.2.6 Summary of hPTH therapy on nephrocalcinosis and nephrolithiasis by ultra sound and CT

The rate of new, stable, and progressing nephrocalcinosis and nephrolithiasis (NC/NL) in study subjects will be summarized.

